#### **5.4.4. Valvular Toxicity Stopping Criteria**

Subjects who have a new asymptomatic, moderate regurgitation or stenosis by echocardiogram (ECHO) (Grade 2 mitral/tricuspid/aortic valvular toxicity per NCI-CTCAE v4.03) should temporarily discontinue GSK2820151 and have a repeat evaluation by ECHO within 1 week. ECHO should be repeated every 1 to 2 weeks for 4 weeks or until valve recovery to baseline.

- If the valve recovers to baseline any time during the next 4 weeks after consultation with and approval from the GSK Medical Monitor, the subject may be restarted on GSK2820151 at a reduced dose(s). For such subjects, monitoring of the valve via ECHO will then be performed 2 and 4 weeks after rechallenge, and every 4 weeks thereafter for 16 weeks and then per protocol.
- If repeat ECHO does not reveal valve recovery to baseline within 4 weeks, then the subject should permanently discontinue GSK2820151. The valve should continue to be monitored via ECHO every 4 weeks for 16 weeks or until resolution.

Subjects with a Grade 3 or 4 (symptomatic, severe regurgitation/stenosis by imaging with symptoms controlled by medical intervention) valvular toxicity must discontinue GSK2820151. Valvular toxicity should continue to be monitored every 4 weeks for 16 weeks or until resolution. If recovery occurs (return to baseline via imaging AND symptom resolution) within 4 weeks, the subject may restart GSK2820151 at a reduced dose after consultation with and approval from the GSK Medical Monitor.

ECHO must be performed at baseline and at the final study visit. Copies of all ECHO(s) and cardiology consultations performed on subjects who experience valvular toxicity will be required by GSK for review. Instructions for submitting qualifying ECHOs are provided in the Study Reference Manual (SRM).

#### **5.4.5. Other Stopping Criteria**

All subjects will require a chest X-ray and pulmonary function testing at screening, as defined in the Time and Events table. Subjects with clinical concern for pneumonitis will be evaluated per institutional practice with input from the GSK medical monitor. For management of suspected pneumonitis, including criteria for dose reduction and discontinuation of therapy, see [Appendix 7](#).

To monitor for thrombocytopenia, CBCs will be drawn twice weekly for the first three weeks of study, weekly for the next two weeks, and then every other week, as described in the Time and Events table. Subjects who develop Grade 2 or greater thrombocytopenia may be monitored more frequently, as clinically indicated. Please see [Appendix 7](#) for suggested management of thrombocytopenia.

Safety will be reviewed on an ongoing basis by the Safety Review Team (SRT) which will be comprised of, at a minimum, a GSK medical monitor, GSK Global Safety representative, and GSK clinical study representative (including a representative from Biostatistics). Deaths, SAEs, and Grade 3/4 adverse events will be carefully evaluated for the possibility of causality.

If clinically significant adverse events or toxicities are observed in more than one third of the subjects, and/or if deaths related to study drug are observed, enrollment may be terminated and/or a lower-dose cohort may be opened or expanded. The final determination will be made by the Sponsor and investigators.

The sponsor may also terminate the study if the safety, pharmacokinetics (PK) or pharmacodynamic (PD) data suggest that an appropriate therapeutic exposure cannot be achieved using the dosing schedules defined in the protocol.

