**Table 3 Dose –Limiting Toxicity Criteria**

Toxicity	DLT Definition
Hematologic	
 
• Grade 4 neutropenia (absolute neutrophil count [ANC] <500/mm^3 for ≥5 days)
 
• Febrile neutropenia (as defined by NCI-CTCAE v4.03 [concurrent Grade 4 neutropenia and fever >38.3°C])
 
• Grade 4 anemia of any duration
 
• Grade 3 thrombocytopenia with clinically significant bleeding or grade 4 thrombocytopenia (platelets <25,000/mm^3)
 

Non-hematologic	
 
• Alanine aminotransferase (ALT) >3x upper limit of normal (ULN) + bilirubin ≥2xULN (>35% direct) or ALT between 3-5 X ULN with bilirubin < 2xULN but with hepatitis symptoms or rash (See Section 5.4.1 for Liver Stopping Criteria)
 
• Grade 3 nausea, vomiting or diarrhea that does not improve within 24h despite appropriate supportive treatment(s)
 
• Grade 4 nausea, vomiting, or diarrhea
 
• Grade 3 hypertensioa (uncontrolled despite addition of up to 2 antihypertensive medications)
 
• Grade 4 hypertension
 
• Grade 3 or greater clinically significant non-hematologic toxicity (including QTc corrected by Fridericia's formula [QTcF]) per NCI-CTCAE, v4.03 except toxicities listed in Section 4.2.5
 
• Grade 2 troponin b elevation (central laboratory >ULN), measured on two separate occasions within 48 hours in order to confirm elevation and with other clinical signs, symptoms, laboratory tests consistent with cardiac toxicityb.
 

Other	
 
• Any toxicity resulting in a dose delay of >14 days of the intended next dose
 
• Grade 2 or higher toxicity that occurs beyond 28 days which in the judgment of the investigator and GSK Medical Monitor is considered to be a DLT
 

Toxicity Grading based on NCI-CTCAE v4.03

- a. Grade 3 hypertension adequately controlled by antihypertensive medication(s) is not considered to be a DLT.
- b. In the event a troponin (central laboratory assessment) is not performed or a laboratory error occurs, considerations for a DLT criterion will involve review of two separate local troponin (I or T) assays done within 48 hours at a local investigator site. Troponin I or T elevations greater than the upper limit of normal, and > 10% coefficient of variance (CV%) for that assay will be considered as a grade 2 elevation.

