
Lymphoid/Hematologic Effects
	
Lymphoid / hematologic toxicity was observed in rats given <math>\geq 3</math> mg/kg/day and in dogs given <math>\geq 5</math> mg/kg/day .
 
The effects manifested as hypocellularity in bone marrow, thymus and lymph nodes of rats and dogs and reduced cellularity of the spleen in rats. This was accompanied peripherally by evidence of increased red cell turnover and/or mild haemolysis, reductions in red blood cells, platelets, basophils, eosinophils, lymphocytes, and increases in neutrophils (in response to GI toxicity). Effects on reticulocyte counts were variable.
 
Regenerative response in blood cell parameters and microscopic observation of extramedullary haematopoiesis and increased cellularity in the lymph nodes and spleen was evident after up to five weeks off dose. Increased activated partial thromboplastin time (APTT) was observed in male rats given <math>\geq 1</math> mg/kg/day and in dogs given
	
ICF includes the risk of lymphoid / hematologic toxicity.
 
Protocol includes laboratory assessments (complete blood count [CBC] and coagulation factors [international normalized ratio (INR), prothrombin time (PT), partial thromboplastin time (PTT)], exclusion criteria if there is evidence of clinically significant bleeding episodes, monitoring for bruising/infection and dose stopping/modifications criteria (refer to Section 14.7.1).

Potential Risk of Clinical Significance	Summary of Data/Rationale for Risk	Mitigation Strategy
	
20 mg/kg/day . A mild decrease in APTT was observed in female rats given 3 mg/kg/day. Increases in fibrinogen was observed in dogs given 20 mg/kg/day. All of these effects were reversible.
	

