## 6. STUDY TREATMENT

### 6.1. GSK2820151

The term ‘study treatment’ is used throughout the protocol to describe the administration of GSK2820151.

	Study Treatment
Product name:	GSK2820151
Formulation description:	GSK2820151 capsules contain 1 mg, 5 mg, 10 mg, 50 mg, or 100 mg of GSK2820151 as free base equivalent
Dosage form:	Capsule
Unit dose strength(s)/Dosage level(s):	1 mg, 5 mg, 10 mg, 50 mg, and 100 mg
Route of Administration	Oral
Dosing instructions:	The dosing regimen is detailed in Table 7 and is designed to permit collection of detailed safety and PK data. 
 
• Week 1: Once daily on days 1, 3, 4, and 5
 
• Week 2: Once daily on days 1, 2, 3, 4, 5
 
• Weeks 3 and beyond: Once daily continuously
 
 GSK2820151 is to be administered orally, once daily, at approximately the same time of day, with no food or antacids for 1 h before and 2 h after each dose
Physical description:	1 mg: Pink, Size 1 capsule 5 mg: Green, Size 1 capsule 10 mg: Swedish Orange, Size 1 capsule 50 mg: White Opaque, Size 0 capsule 100 mg: Blue Opaque, Size 0 capsule

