Concomitant medications		continuous from signing of informed consent																											
Laboratory assessments: For details please see following tables																													
Tests		X	X	X				X		X					X		X		X		X	X	X	X	X	X	X	X	
Cardiac Monitoring																													
Echocardiogram	Within 35 days of first dose	X																			X		X			X		X	
12-lead ECGs	Triplicate SCR ECGs within 35	X	O	O	X			O	X	X	X			O		X	X	X	O	X	X	X	X	X	X	O	X	X	X

Assessments	Notes	S C R	Refer to Section 8.4.2 for visit windows.																				E O T				
			Week 1							Week 2							W3		W4		W5	W7		W9	q4W	q8W	
			D 1	D 2	D 3	D 4	D 5	D 6	D 7	D 1	D 2	D 3	D 4	D 5	D 6	D 7	D 1	D 4	D 1	D 4	D 1	D 1		D 1	D 1	D 1	
(Triplicate)	days of first dose. For timing of triplicate ECGs on O days, see Table 9 and Table 10 . Otherwise, triplicate ECGs at approximately same time of day, and prior to dose on dosing days. If QTcF increase >30msec, ECGs daily through W2.			X																							
Holter monitoring	At least 24 h, on dosing days start at least 60 min predose.	X	X				X										X						X				
Telemetry	Start at least 60 min predose and for at least 48 h.		X	X																							
Efficacy																											
Cross-sectional (Computed tomography [CT] or magnetic resonance imaging [MRI]), functional (Positron emission tomography [PET]), or nuclear (bone scan) imaging	Appropriate imaging modality should be selected by the investigator depending on disease histology and location. SCR assessment within 2 weeks of first dose. Target lesions to be identified at SCR and followed. See Section 14.8.1 for guidelines.	X																						X		X	X
Pharmacokinetics (PK) and Pharmacodynamics (PD): For details please see Table 9 and Table 10																											
PK and biomarker samples			X	X			X					X					X						X				
Samples for		X	X	X												X										X	

Assessments	Notes	S C R	Refer to Section 8.4.2 for visit windows.																				E O T			
			Week 1							Week 2							W3		W4		W5	W7		W9	q4W	q8W
			D 1	D 2	D 3	D 4	D 5	D 6	D 7	D 1	D 2	D 3	D 4	D 5	D 6	D 7	D 1	D 4	D 1	D 4	D 1	D 1		D 1	D 1	D 1
mRNA																										
LPS blood sample			X																							
PK Urine samples			X														X									
Pharmacogenomics (PGx)																										
PGx sample			X																							
FOLLOW-UP PHASE																										

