**Table 8 Time and Events: Laboratory Assessments**

NB: On dosing days, collect blood samples prior to dosing. W1D1 samples not needed if SCR sample collected within 72h of first dose.	Notes	SCR	W1			W2		W3	W4	W5	W7	W9	q4W	q8W	EOT
			D1	D2	D6	D1	D6	D1	D1	D1	D1	D1	D1	D1	
Troponin, NT-proBNP-9	W1D1, W1D2: local lab sample 3X/24h; central lab sample 1X/24h. All other timepoints including unscheduled collect 2 samples: 1 for local, 1 for central lab	X	X	X	X	X	X	X	X	X		X		X	X
Hematology		X	X		X	X	X	X 	X	X	X	X	X		X
Clinical chemistry		X	X		X	X	X	X	X	X	X	X	X		X
Pancreatic		X	X		X	X		X		X	X	X	X		X
Coagulation		X	X		X	X		X		X	X	X	X		X
Factor VII Assay	Also perform if PT, INR or aPTT are $\geq 1.5 \times \text{ULN}$ , or in case of bleeding event	X						X		X					
Creatine phosphokinase		X	X		X	X		X		X	X	X	X		X
Liver chemistry		X	X		X	X	X	X	X	X	X	X	X		X
Fasting blood glucose and insulin	Will be performed at central lab if not available at local lab	X	X		X	X		X		X	X	X	X		X
c-peptide and 1,5 -Anhydroglucitol (1,5 AG)	Will be performed at central lab if not available at local lab	X	X							X		X		X	
Hemoglobin A1c		X	X							X		X		X	
Fasting lipids		X	X							X		X		X	X
Thyroid monitoring	Thyroid stimulating hormone (TSH), free T3, free T4. If TSH is abnormal at W1D1, continue monitor TSH, free T3 and free T4 going forward	X	X							X		X		X	X

NB: On dosing days, collect blood samples prior to dosing. W1D1 samples not needed if SCR sample collected within 72h of first dose.	Notes	SCR	W1			W2		W3	W4	W5	W7	W9	q4W	q8W	EOT
			D1	D2	D6	D1	D6	D1	D1	D1	D1	D1	D1	D1	
Urinalysis		X	X							X		X		X	X
Pregnancy test, females	Serum pregnancy test within 7 days of first dose; urine or serum test thereafter	X	X							X		X	X		X
Testosterone, males	Complete and free testosterone at SCR; free testosterone thereafter	X	X							X		X	X		X
CK, CK-MB	Predose and 12-18 h post dose		X	as clinically appropriate											
Safety Cytokines	This is collected as part of the Predose PK sample and is sent to Myriad via Covance.	X	as clinically appropriate following fever												
HBsAg, HepC antibody	If hepatitis C antibody positive, perform third generation immunoassay on same sample to confirm results	X													

C=cycle; D=day; EOT=End of Treatment Visit; q4W=Every 4 weeks; q8W=every 8 weeks; SCR=Screening; W=week

1. If any parameter (i.e., platelets) shows a downward trend, additional analyses should be performed within 2-3 days to monitor.

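### Section 5.4.5 promises a platelet-count schedule that Table 8 does not contain: one count short in Week 3, and every 4 weeks instead of every 2 after Week 9

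*Protocol*

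**What the plan says.** Protocol Section 5.4.5 sets the platelet monitoring: "CBCs will be drawn twice weekly for the first three weeks of study, weekly for the next two weeks, and then every other week". It presents this as the schedule already in the Time and Events table. Section 8 likewise sends the reader to that table for the exact timing of every assessment.

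Table 11 lists the platelet count under hematology. The hematology row of Table 8 is marked at screening, W1D1, W1D6, W2D1, W2D6, W3D1, W4D1, W5D1, W7D1 and W9D1, then every 4 weeks and at end of treatment. In Table 7 the laboratory block ("Laboratory assessments: For details please see following tables") has no mark in its Tests row at W3D4.

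The W3D1 mark carries footnote 1: "If any parameter (i.e., platelets) shows a downward trend, additional analyses should be performed within 2-3 days to monitor". The header of Table 8 adds: "On dosing days, collect blood samples prior to dosing".

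On dosing, Section 6.1 gives Days 1, 3, 4 and 5 in Week 1. It continues "Week 2: Once daily on days 1, 2, 3, 4, 5" and then "Weeks 3 and beyond: Once daily continuously".

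Table 3 counts "Grade 3 thrombocytopenia with clinically significant bleeding or grade 4 thrombocytopenia" as a DLT. Section 4.6.1 reports "reductions in red blood cells, platelets, basophils, eosinophils, lymphocytes" in the animal studies.

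**The concern.** A stated safety-monitoring rule does not match the table it cites. A site that works from the table will not make all the draws that Section 5.4.5 says will be made.

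Week 3 matters more than the later mismatch, for three reasons:

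- It lies inside the 4-week DLT window.
- It is when dosing rises from 4-5 doses a week to 7.
- Platelet loss is an identified risk, and Table 3 sets no minimum duration for Grade 4 thrombocytopenia. Under Table 12, Grade 3 already requires the drug to be withheld, so a later count can mean a later hold.

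In the accelerated phase a cohort may be a single subject, and four clean weeks permit an increase of up to 100% (Section 4.2.2, Table 1). What is seen in that window feeds directly into the dose decision.

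After Week 9 the mismatch is a routine monitoring inconsistency, not a DLT question.

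There is also a reporting consequence. SAP Section 9.2 lists all protocol deviations, and the documents leave open which schedule defines a missed blood count.

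**Working it through.** No power or sample-size figure is involved. The check sets the two schedules side by side in nominal study days.

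**Scheduled counts**

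| Period | Section 5.4.5 | Table 8 |
|---|---|---|
| Week 1 | 2 | 2 (D1, D6) |
| Week 2 | 2 | 2 (D1, D6) |
| Week 3 | 2 | 1 (D1, footnote 1) |
| Week 4 | 1 | 1 |
| Week 5 | 1 | 1 |
| Weeks 7 and 9 | 1 each | 1 each |
| After Week 9 | every 14 days | every 28 days |

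The rows differ only in Week 3 and after Week 9.

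**Counts in Days 1-28**

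- Section 5.4.5: 2 × 3 weeks + 1 in Week 4 = 7.
- Table 8: Days 1, 6, 8, 13, 15 and 22 = 6. W5D1 is Day 29 and falls outside. W1D1 is counted as drawn, although a screening sample within 72 hours may replace it.

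**Cumulative counts**, taking the four-weekly draws as Weeks 13, 17 and so on: 8 versus 7 through Week 5, 10 versus 9 through Week 9, 18 versus 13 through Week 25, and 32 versus 20 through Week 53 (Section 5.4.5 first in each pair).

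**Doses between successive Table 8 counts.** Dosing days from Section 6.1 are Days 1, 3, 4, 5; Days 8-12; then daily from Day 15. Samples on dosing days are taken before the dose.

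| Interval | Doses given | Number |
|---|---|---|
| Day 1 to 6 | Days 1, 3, 4, 5 | 4 |
| Day 6 to 8 | none | 0 |
| Day 8 to 13 | Days 8-12 | 5 |
| Day 13 to 15 | none | 0 |
| Day 15 to 22 | Days 15-21 | 7 |

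The Week 3 gap is 22 − 15 = 7 days.

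**What footnote 1 can see.** The last Week 2 dose is on Day 12, so W3D1 comes 15 − 12 = 3 days after it and before the first continuous dose. The trend that triggers the repeat is therefore judged before any continuous dosing has been given.

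**Effect of a W3D4 count.** W3D4 is Day 18. A pre-dose draw then splits the 7 doses into 3 (Days 15-17) and 4 (Days 18-21).

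**Extraction damage?** Unlikely. The hematology row is the same in the original protocol and in the Amendment 4 change log.

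**The case against.** The strongest reply is that sites have a governing source. Section 5.4.5 defers to the table and Section 8 makes adherence to it essential, so the fault is an inaccurate prose summary that editing one sentence would cure. That is fair as a description: this is mainly an internal inconsistency. It does not settle which schedule the sponsor meant, and following the table drops a count that the safety section says will be taken.

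Second, footnote 1 can put a repeat at about Days 17-18, just where the extra draw is wanted, and by W3D1 up to five counts and nine doses are available for judging a trend. This narrows the gap but does not close it: the repeat is conditional, and the condition is assessed before continuous dosing begins.

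Third, both texts accept 7 days and 7 doses between counts from Day 22 to Day 29, so neither treats that interval as unsafe in itself. This stands. What remains is that Week 3 is the first such week.

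Fourth, no DLT is shown to be missed. Platelets would have to fall below the Grade 4 threshold and recover between Day 15 and Day 22 while daily dosing continued, and the documents give no time course suggesting that. This also stands; a persistent low count would be found on Day 22. Later detection is the more realistic effect.

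Finally, Table 12 calls for weekly or more frequent monitoring of Grade 1-2 counts, and Section 5.4.5 allows more frequent counts from Grade 2. That softens the post-Week 9 mismatch once thrombocytopenia is known, but does not reconcile the routine schedules.

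**Conclusion.** The concern holds. The schedule in Section 5.4.5 is not the one in Tables 7 and 8. The size is one scheduled count in the DLT window (6 instead of 7), in the first week of continuous dosing, and a 28-day instead of a 14-day interval after Week 9. It should be corrected, mainly because of Week 3; the later difference needs only consistent wording.

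The day and dose counts assume nominal visits. Assessments in Weeks 2-9 may move by 3 days either way (Section 8.2.2), and W3D4 sampling has a window of +2 days on the standard schedule (Table 10), so actual gaps and the 3/4 split can differ. SAP Section 1 reports that the study ended early with 5 subjects enrolled, so a correction cannot change care in this study. It matters for how missed counts are classified and for any later protocol that reuses the schedule.

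**What to change.** - **Week 3:** add a hematology mark at W3D4 in Table 8 and a matching mark in the Tests row of Table 7. On the standard schedule this is Day 18, which Section 7.2 already names as a serial PK sampling day. Keep footnote 1.
- **After Week 9:** change Section 5.4.5 to follow the monthly visits in Section 8.2.2: twice weekly in Weeks 1-3, weekly in Weeks 4 and 5, at Weeks 7 and 9, and every 4 weeks thereafter.

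The cost is amendment wording plus one local blood count per subject at an existing visit, with no added test or visit after Week 9.

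If the sponsor prefers not to add the draw, the least that is needed is to rewrite Section 5.4.5 to match Table 8: twice weekly in Weeks 1-2, weekly in Weeks 3-5 with the conditional repeat in Week 3, at Weeks 7 and 9, then every 4 weeks. That removes the contradiction but leaves the first week of continuous dosing with no unconditional count between Day 15 and Day 22.

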## **5.5. Subject and Study Completion**

A completed subject is one who has discontinued study treatment for reasons listed in Section [5.4](#) and completed a post-treatment follow-up visit or has died while receiving study treatment.

A subject will be considered to have completed the study 2 years after the last treatment or if the subject dies or is still receiving study treatment or in follow-up at the time the study is closed or terminated, whichever is sooner. Document the cause of death in the eCRF. The End of Study eCRF should only be completed when a subject is no longer being followed. The end of the study is defined as the last subject's last visit.

## 6. STUDY TREATMENT

### 6.1. GSK2820151

The term ‘study treatment’ is used throughout the protocol to describe the administration of GSK2820151.

	Study Treatment
Product name:	GSK2820151
Formulation description:	GSK2820151 capsules contain 1 mg, 5 mg, 10 mg, 50 mg, or 100 mg of GSK2820151 as free base equivalent
Dosage form:	Capsule
Unit dose strength(s)/Dosage level(s):	1 mg, 5 mg, 10 mg, 50 mg, and 100 mg
Route of Administration	Oral
Dosing instructions:	The dosing regimen is detailed in Table 7 and is designed to permit collection of detailed safety and PK data. 
 
• Week 1: Once daily on days 1, 3, 4, and 5
 
• Week 2: Once daily on days 1, 2, 3, 4, 5
 
• Weeks 3 and beyond: Once daily continuously
 
 GSK2820151 is to be administered orally, once daily, at approximately the same time of day, with no food or antacids for 1 h before and 2 h after each dose
Physical description:	1 mg: Pink, Size 1 capsule 5 mg: Green, Size 1 capsule 10 mg: Swedish Orange, Size 1 capsule 50 mg: White Opaque, Size 0 capsule 100 mg: Blue Opaque, Size 0 capsule

### 6.2. Treatment Assignment

Subjects will be assigned to receive GSK2820151 in an open-label fashion. There will be no placebo arm.

### 6.3. Packaging and Labeling

GSK2820151 will be provided to the sites by GSK. The contents of the label will be in accordance with all applicable regulatory requirements.

### 6.4. Preparation/Handling/Storage/Accountability

No special preparation of study treatment is required.

- Only subjects enrolled in the study may receive study treatment and only authorized site staff may supply or administer study treatment. All study treatments must be stored in a secure environmentally controlled and monitored (manual or automated)

area in accordance with the labelled storage conditions with access limited to the investigator and authorized site staff.

- The investigator, institution, or the head of the medical institution (where applicable) is responsible for study treatment accountability, reconciliation, and record maintenance (e.g., receipt, reconciliation, and final disposition records).
- Further guidance and information for final disposition of unused study treatment are provided in the Laboratory Manual.

Precaution will be taken to avoid direct contact with the study treatment. A Material Safety Data Sheet (MSDS) describing occupational hazards and recommended handling precautions will be provided to the investigator. In the case of unintentional occupational exposure notify the monitor, Medical Monitor or GSK study contact.

Limited exposure and precautionary action (example: wearing gloves, washing hands post exposure, etc.) should be taken by site staff dispensing GSK2820151.

